8.1 Statistical Principles

Mean, standard deviation (sd) and any other statistical measures, will be reported to one decimal place. Continuous data will be summarised in the form of means, sd, median, interquartile range (IQR) and range as appropriate. Categorical data will be summarised using the frequencies and proportions. Chi-squared and t-tests will be performed to compare the frequency of dichotomous variables and the values of continuous variables where relevant. 95% CIs will be reported for main effect sizes. Statistical significance will be assessed using $p < 0.05$. Actual p-values will be reported except for p-values less than 3 decimal places which will be reported as “ < 0.001 ”. P-values > 0.1 will be reported to one decimal place, p-values between 0.01 and 0.1 will be reported to 2 decimal places, and p-values between 0.001 and 0.01 will be reported to three decimal places.

The assessment of any associations with baseline characteristics and the outcomes of interest (objectives 2-5) will be assessed using logistic regression (prevalent and incident outcomes), Cox proportional hazards (time to event outcomes) and Poisson regression (repeated event outcomes) models. Three different adjustment sets will be used for each endpoint analysis. These include: an unadjusted model, a sex and age adjusted model, and a multivariable model with an adjustment set of: age, sex, BMI, smoking status, alcohol use, and common comorbidities: type 2 diabetes, hypertension, atrial fibrillation, angina, acute myocardial infarction, stroke, heart failure, chronic liver disease, dementia, rheumatoid arthritis, asthma, chronic obstructive pulmonary disease, chronic kidney disease stages 3-5, malignancy and inflammatory bowel disease.

Assumptions of statistical approaches will be assessed, and transformations used if necessary.

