7.3 Matching Process

For objectives 2-5, controls for each vitiligo case will be identified from the pool of people without a vitiligo diagnosis registered in the OPCRCD database at the time of vitiligo diagnosis for the case. Vitiligo cases will be eligible as controls up until the date of their vitiligo diagnosis (at which date their follow-up will be censored if selected as a control).

Each case will be assigned an index date at the time of their vitiligo diagnosis. Corresponding controls assigned to each case will have the same index date.

Each individual with vitiligo will be matched at their index date with up to four unaffected controls. Controls cannot be diagnosed with vitiligo at the date of matching and will require at least one year of follow-up time to minimise the risk of a non-recorded existing diagnosis of vitiligo. Time-updated exact matching will be performed by age, sex, ethnicity and deprivation, selected from the pool of eligible people registered in the same GP practice.

If required, a combination of time-dependent propensity score matching and exact matching will be performed to create a baseline matched dataset.

The matching process is subject to change depending on the feasibility of the mentioned matching process during the initial exploration of the data. The produced baseline matched dataset will be used for all analyses for objective 2-5.

8. Statistical Analysis

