8.3 Secondary Endpoint Analysis

Objective 2

Anxiety and depression outcomes will be captured if occurring prior to, or within two years of, an individuals' study index date. Binary outcome logistic regression model outputs will be used to compare the burden of anxiety and depression in vitiligo cases compared to matched controls. Furthermore, additional analyses for new onset anxiety and depression outcomes will be conducted, excluding people with a previous record of the respective mental health condition. Anxiety and depression outcomes will be defined by the first occurrence of a relevant code in the primary care record up to two years post index-date. Cox proportional hazards regression will be used to estimate the excess risk of anxiety and depression outcomes in vitiligo cases versus controls. Results will be described as hazard ratios.

Objective 3

Parasuicide/suicide attempts will be defined by the first occurrence of a relevant code in the primary care record up to two years post index-date. People with a previous record of parasuicide/suicide attempt will be excluded from the calculations. Cox proportional hazards regression will be used to estimate the excess risk of parasuicide/suicide attempts in vitiligo cases versus matched controls. Results will be described as hazard ratios.

Adjustment disorder and sleep disturbance will be defined by the first occurrence of a relevant code in the primary care record up to two years post index-date. People with a previous record of the adjustment disorder will be excluded from the from the adjustment disorder endpoint analysis. Cox proportional hazards regression will be used to estimate the excess risk of the relevant condition in vitiligo cases versus matched controls. Results will be described as hazard ratios.

Objective 4

Dermatology referral and mental health referral or reviews will be defined by the first occurrence of a relevant code in the primary care record up to two years post index date. Cox proportional hazards regression will be used to estimate the excess risk of these outcomes in vitiligo cases versus matched controls.

For primary care encounters reviews, defined as a rate of encounters within two years after the index date, will be compared using generalised linear models with time-at-risk as an offset. Results will be described as incidence rate ratios.

Objective 5

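### The plan gives no dispersion rule for primary care visit counts; a plain Poisson fit, which complies with the plan, would probably give rate-ratio intervals that are too narrow

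*Combined protocol and SAP*

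**What the plan says.** Section 8.1 (Statistical Principles) allocates model types by outcome type. Repeated events go to "Poisson regression (repeated event outcomes) models". Section 8.3, Objective 4, analyses one outcome of that kind, primary care encounters, "defined as a rate of encounters within two years after the index date". These "will be compared using generalised linear models with time-at-risk as an offset", and "Results will be described as incidence rate ratios". No family is named there.

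The only general safeguard is in 8.1: "Assumptions of statistical approaches will be assessed, and transformations used if necessary". The same section says "95% CIs will be reported for main effect sizes" and sets significance at p below 0.05. It calls for three versions of each endpoint model: unadjusted, adjusted for age and sex, and multivariable.

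Under section 7.3 each case is "matched at their index date with up to four unaffected controls", drawn from the same practice. No section says how standard errors are obtained, whether over-dispersion will be checked, or what replaces Poisson if it is found. Section 6 covers anxiety and depression only, so the plan contains no mean, standard deviation or dispersion for visit counts.

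**The concern.** A Poisson model takes the variance of the count to equal its mean. For visits to a practice that requires everyone with the same covariates to consult at the same underlying rate. The plan's own content makes this unlikely:

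- Section 8.4 anticipates controls who are registered but never attend.
- Sections 7.1 and 7.2 admit people from age 13, with follow-up to age 95.
- The unadjusted and age-sex models in 8.1 leave out the 15 comorbidities that the multivariable model includes, so differences in illness remain in the residual variation.

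If the variance exceeds the mean, model-based Poisson standard errors are too small, intervals are too narrow and p-values too low. Transformation is no cure. Transforming the count abandons the offset rate model and the incidence rate ratio that 8.3 promises, and it leaves the variance assumption of a Poisson fit where it was. At stake is how far the visit rate ratios can be trusted, both overall and within each age, sex, deprivation and ethnicity group.

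**Working it through.** The plan states no figure for this analysis, so there is none to reproduce. The check asks what a plain Poisson variance would do.

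**From the documents.** Poisson for repeated events, 5% significance and 95% intervals (8.1; taken as two-sided); rate ratio over two years (8.3); up to four controls per case (7.3); 8,000 anticipated cases (section 6).

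**Assumed.** The variance-to-mean ratio φ, and the mean number of visits μ where one is needed.

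**Step 1: effect on error rates.** True SE = √φ × Poisson SE. So the actual two-sided error is 2 × [1 − Φ(1.96/√φ)], coverage is its complement, and interval width relative to the correct width is 1/√φ. For an unadjusted, unmatched comparison:

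| φ (assumed) | √φ | Relative width | Coverage | Type I error |
|---|---|---|---|---|
| 1 | 1.00 | 100% | 95.0% | 5.0% |
| 1.5 | 1.22 | 82% | 89.0% | 11.0% |
| 2 | 1.41 | 71% | 83.4% | 16.6% |
| 3 | 1.73 | 58% | 74.2% | 25.8% |
| 5 | 2.24 | 45% | 61.9% | 38.1% |
| 9 | 3.00 | 33% | 48.6% | 51.4% |

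**Step 2: can φ plausibly exceed 1?** Suppose a share p of each group never attends and everyone else is exactly Poisson with mean 8. Then φ = 1 + 8p. For p = 10%, φ = 1.8 and the error is 14%; for p = 20%, φ = 2.6 and the error is 22%. If personal rates follow a gamma distribution with shape k, φ = 1 + μ/k. With μ = 8 and k = 4, φ = 3. If the four-year sensitivity analysis in 8.4 doubles μ to 16 at the same k, φ = 5, and the error goes from 26% to 38%.

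**Step 3: simulation.** Gamma-Poisson counts, 500 cases and 2,000 controls, true rate ratio 1, 1,500 runs per setting, means of 6, 10 and 16 visits, k from 0.5 to 5 (φ from 2.2 to 33). Plain Poisson rejected in 17.6% to 72.9% of runs. Robust or dispersion-scaled standard errors rejected in 3.7% to 5.5%.

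**Step 4: matching.** If a fraction s of the extra-Poisson variance is shared within matched sets, the variance of the case-control contrast scales with 1 + (φ − 1)(1 − s) in place of φ. With φ = 3 and s = 0.5 (both assumed) this is 2, and the error falls from 25.8% to 16.6%. It returns to 5% only if s = 1, that is, if people within a set do not differ at all in underlying rate. A simulation of 400 sets at 1:4, mean 8, with gamma shapes of 2 to 4 for the set and personal components, gave 28% to 42% for plain Poisson.

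**Step 5: absolute size.** Take μ = 8, φ = 9 and four controls for every case.

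- All 8,000 cases: Poisson SE of the log rate ratio = √(1/64,000 + 1/256,000) = 0.0044. The 95% half-width is 0.9%; multiplied by √9 it is 2.6%.
- An illustrative stratum of 400 cases: SE = √(1/3,200 + 1/12,800) = 0.0198. The half-width on the log scale is 0.039; multiplied by 3 it is 0.116.

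**The case against.** The strongest reply is that the plan does not commit to a wrong variance. Section 8.3, the endpoint-specific text, leaves the family open, so quasi-Poisson would fit its wording and so, read broadly, would negative binomial. Poisson regression with sandwich errors is still Poisson regression. Section 8.1 promises an assumption check, and variance equal to the mean is the central assumption to check. The multivariable model and the matching would absorb some heterogeneity. All of this stands. It shows that a correct analysis is permitted, but not that one is specified: the only family named is Poisson and the only remedy named does not work.

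A reader might go further and infer that the intervals will certainly be far too narrow and that false subgroup disparities will be declared. The documents do not support that, for three reasons.

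- No dispersion is given. A large distortion needs φ of several units, which the plan neither states nor rules out.
- Section 8.3 sets out case-versus-control rate ratios and names no formal test between subgroups. The direct error is in each rate ratio. False disparities follow only if strata are compared on these intervals or p-values.
- Section 4.5 lists primary care visits beside dermatology and mental health referrals without ranking them, so visits cannot be called the main utilisation measure.

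**Conclusion.** The concern holds as a gap in specification with a predictable direction. For any variance-to-mean ratio above 1, a plain Poisson fit that complies with the plan gives intervals that are too narrow, and the plan's own population makes a ratio above 1 likely. Even a ratio of 1.5 roughly doubles the nominal error, to 11%; a ratio of 3 gives 26% and one of 9 gives 51%. These figures are conditional on the assumed dispersion and on an unadjusted, unmatched comparison. Adjustment and matching may lower them by an amount the documents do not allow one to compute.

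Over-dispersion does not bias the rate ratio itself. In the full cohort the absolute change in the interval is small; in small strata it could alter a conclusion. Visits are one endpoint of a secondary, descriptive objective, and the primary lifetime-risk analysis is untouched. This should be fixed, but it does not threaten the study.

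**What to change.** In 8.1 and 8.3, name one method for primary care encounters and use the same wording in both places. Either of these would do:

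- negative binomial regression with log time-at-risk as the offset; or
- a Poisson mean model with the same offset and robust standard errors clustered on the matched set.

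Apply it to the overall and all subgroup visit rate ratios, under all three adjustment sets and in the section 8.4 sensitivity analyses. State that transformation will not be used for this outcome, because it would lose the rate ratio.

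The cost is a few lines of SAP wording, a small change to the R code and wider intervals. No extra data are needed. The choice is best made before the visit data are examined.

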8.4 Sensitivity Analysis

To evaluate the magnitude of potential bias from including, as matched controls, people who are registered with GP practices but who do not attend their practice, we will also repeat the primary analysis for mental health, healthcare utilisation and work-related outcomes including only matched controls with at least one primary care encounter in the year preceding their index date.

We will also repeat the primary analysis for mental health, healthcare utilisation and work-related outcomes extending the outcome period to four years.

To assess the impact of missing ethnicity data, we will repeat the ethnicity sociodemographic subgroup analysis amending missing ethnicity entries to white.

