8.5 Missing Data

These studies will use the missing indicator variable method as missing data are considered likely not to be missing at random, meaning multiple imputation approaches will lack validity.

Patients will need to be excluded from analyses based on a matched design if they have incomplete data in the fields (age, sex) required to run the matching process. In similar studies, the exclusion rate due to incomplete data has been very low. (23, 24)

How missing data is handled will be dependent on exploratory and sensitivity analyses and is subject to change.

9. Study Limitations

Disparities between sociodemographic subgroups will be interpreted based on the assumption of the primary/secondary outcomes being related to the vitiligo. We have no definite way to identify that every occurrence of an outcome is related to vitiligo in the context of healthcare utilisation and work impact outcomes and therefore causal interpretation is not possible.

This is an ecological study limited to the UK population and may not be generalisable to other populations.

We expect some missing data for the ethnicity variable, this is a limitation of the dataset itself and could result in bias. Necessary sensitivity analyses will be undertaken to circumvent this and limit any impact this could have in interpretation of results in our analysis.

We expect low number of occurrences for the outcomes of referrals for adjustment disorder and parasuicide/suicide, thus reporting of the results for these two endpoints will depend on the sufficiency of numbers available.

10. Statistical Software

All statistical analyses will be performed using R version 4.2.3 or higher.

11. Ethics

The study will be conducted in accordance with legal and regulatory requirements, as well as with scientific purpose, value and rigor and follow generally accepted research practices described in:

- Guidelines for Good Pharmacoepidemiology Practices (GPP). Public Policy Committee, International Society of Pharmacoepidemiology. Pharmacoepidemiology and Drug Safety 2016; 25:2-10.
- Good Practices for Outcomes Research issued by the International Society for Pharmacoeconomics and Outcomes Research (ISPOR)
- Good practices for real-world data studies of treatment and/or comparative effectiveness: Recommendations from the joint ISPOR-ISPE Special Task Force on real-world evidence in health care decision making

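### The adjusted models for Objectives 2–5 omit ethnicity and deprivation, so pooled ratios can be modestly confounded if the number of controls per case varies with those factors

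*Combined protocol and SAP*

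**What the plan says.** Section 7.3 states that "Time-updated exact matching will be performed by age, sex, ethnicity and deprivation", with controls drawn from the case's own practice. Each case is "matched at their index date with up to four unaffected controls". The same section allows a propensity-score element and adds: "The matching process is subject to change depending on the feasibility of the mentioned matching process".

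Section 8.1 gives three adjustment sets for every endpoint in Objectives 2–5: none, age and sex, and "a multivariable model with an adjustment set of: age, sex, BMI, smoking status, alcohol use, and common comorbidities". The models named are logistic, Cox and Poisson. No weighting, conditioning on the matched set or clustering is described.

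Two later steps remove people after matching. In Section 8.3 the new-onset anxiety and depression analyses are run "excluding people with a previous record of the respective mental health condition"; parasuicide and adjustment disorder have similar exclusions. The Section 8.4 sensitivity analysis is repeated "including only matched controls with at least one primary care encounter in the year preceding their index date", which filters controls but not cases.

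Section 5 says that an overall result will be published, together with results stratified by age, sex, deprivation and ethnicity.

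**The concern.** Of the factors used for matching, the adjusted models take up only age and sex again. Balance on ethnicity and deprivation therefore rests on the matching alone. Matching secures it in an unweighted analysis only while every case keeps the same number of controls, or while any shortfall is unrelated to those factors.

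The plan leaves four routes to a shortfall that is related to them: the ceiling of four controls, under exact matching inside one practice; the prior-record exclusions, which remove individuals and not sets; the control-only filter in Section 8.4; and a matching process that may change. If the affected factor also predicts the outcome, the overall ratio and the age- and sex-stratum ratios are confounded by it. An ethnicity stratum is safe from confounding by ethnicity but not by deprivation, and the reverse holds for deprivation strata. Sociodemographic disparity is the subject of these objectives, so these two factors deserve direct protection.

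**Working it through.** The plan gives no figure for this point, so there is none to reproduce. All inputs below are assumptions except the ceiling of four controls (Section 7.3) and the 8,000 cases (Section 6).

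**Varying ratio, unadjusted model.** Let p be the share of cases in a harder-to-match group, m its controls per case (4 elsewhere), and RR the group's outcome risk relative to the rest. Vitiligo has no effect. The group's share of controls is q = pm/(pm + 4(1−p)), and the apparent ratio is (p·RR + 1−p)/(q·RR + 1−q). With p = 0.2 and RR = 1.5:

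| m | q | apparent ratio |
|---|---|---|
| 4 | 0.80/4.00 = 0.200 | 1.1000/1.1000 = 1.000 |
| 3.5 | 0.70/3.90 = 0.179 | 1.1000/1.0897 = 1.009 |
| 3 | 0.60/3.80 = 0.158 | 1.1000/1.0789 = 1.020 |
| 2 | 0.40/3.60 = 0.111 | 1.1000/1.0556 = 1.042 |

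The direction can reverse: with RR = 0.8 and m = 2 the ratio is 0.9600/0.9778 = 0.982.

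**After covariate adjustment.** A simulation used 1,000 cohorts of 8,000 cases, 15% risk among cases, no vitiligo effect, and the same p and RR. One binary covariate (prevalence 30% and 60% in the two groups) carried half of the group's log-odds. Mean odds ratios, with the rejection rate at 5% in brackets:

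| m | unadjusted | covariate | covariate + group |
|---|---|---|---|
| 4 | 1.000 (0.038) | 1.000 (0.045) | 1.000 (0.046) |
| 3.5 | 1.011 (0.063) | 1.006 (0.059) | 1.000 (0.047) |
| 3 | 1.023 (0.091) | 1.011 (0.059) | 1.000 (0.047) |
| 2 | 1.050 (0.269) | 1.025 (0.111) | 1.001 (0.043) |

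If the covariate carries none of the group effect, the m = 2 row is 1.051, 1.049 and 1.001.

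**Section 8.3 exclusions.** Start at 4:1 everywhere. Assume prior records in 25% of the group's cases and 20% of its controls, against 18% and 15% elsewhere. Then p = 0.150/(0.150 + 0.656) = 0.186 and q = 0.160/(0.160 + 0.680) = 0.190, giving 0.998 at RR 1.5. With 30% or 40% of the group's cases excluded the ratio is 0.993 or 0.984.

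**Section 8.4 filter.** If 75% or 60% of the group's controls attended, against 85% elsewhere, q = 0.181 or 0.150 and the ratio is 1.009 or 1.1000/1.0750 = 1.023.

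**Changed matching.** If, hypothetically, only age and sex were matched and the group made up 20% of cases but 15%, 10% or 5% of controls, the ratio would be 1.023, 1.048 or 1.073.

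**Dependence on the assumptions.** Shares of 10–40%, 1 to 3.5 controls per case and group risks of 15% v 10%, 10% v 15% or 20% v 10% give unadjusted odds ratios from 0.90 to 1.26. The extremes need a 40% share and one control per case in the group.

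**Parameter count.** The multivariable model has at least 20 terms: age, sex, BMI, smoking, alcohol and 15 comorbidities. Ethnicity adds 4, its missing category 1 and IMD quintile 4, making 29. At an assumed two-year risk of 0.1–0.5% in 8,000 cases and 32,000 controls (a full 4:1), there are 40–200 events. Events per parameter fall from 2–10 (divide by 20) to 1.4–6.9 (divide by 29).

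**The case against.** The strongest reply is that matching in a cohort needs no further adjustment when the ratio is constant, and the calculation agrees: 1.000 at 4:1. A second is that the multivariable model may already absorb part of any imbalance. At 3 or 3.5 controls its rejection rate is 0.059, which the Monte Carlo error (about 0.007) does not separate from 5%. A third is that ethnicity and deprivation strata are protected against their own factor. All three stand, and they keep the point modest. They do not restore protection for the overall, age-stratum and sex-stratum ratios if the ratio varies.

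Some stronger readings are tempting but not supported:

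- A reader might infer that the analysis is biased as written. The documents do not show that controls per case will vary with ethnicity or deprivation.
- A reader might take Section 8.5, which excludes patients from matched analyses "if they have incomplete data in the fields (age, sex) required to run the matching process", as proof that ethnicity is not really matched. That section also plans a missing-indicator method, so missing ethnicity may simply be a matching level of its own. One clarifying sentence would settle it.
- A reader might infer that intervals are too narrow because no clustered variance is named. This is not demonstrated; the unadjusted 4:1 run rejects at 0.038, which is below nominal.
- Overdispersion in primary care encounter counts is a separate matter and lends no weight here. Section 8.1 names Poisson, but Section 8.3 speaks only of generalised linear models, which leaves room for another family, and 8.1 promises assumption checks.

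**Conclusion.** The point holds as a conditional weakness and a cheap improvement, not as a demonstrated error. If controls per case vary with ethnicity or deprivation, and that factor predicts the outcome, the overall and the age- and sex-stratum ratios for Objectives 2–5 can be modestly confounded in either direction. With 20% of cases in the affected group and a group risk ratio of 1.5, a true ratio of 1 appears as about 1.01 to 1.04 unadjusted for 3.5 down to 2 controls there. It moves less after covariate adjustment to the extent that the covariates carry the group effect, and not at all if the ratio is constant. The real size cannot be found from the documents. For scale, 1.042 on the 15% anxiety background in Section 6 is about 0.6 percentage points, against a stated detectable difference of 1.11 points.

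**What to change.** - **Adjusted models.** Add ethnicity (with its missing category) and IMD quintile to both the age-and-sex and the multivariable model. Within ethnicity strata leave out ethnicity; within deprivation strata leave out IMD quintile.
- **Standard errors.** Cluster on practice; matched sets are nested within practices under Section 7.3. Clustering alters the variance only and does not remove confounding by practice.
- **Unadjusted model and rare outcomes.** Drop sets left without a case or without a control, then weight each remaining control by 1/(controls remaining in its set). Every set then contributes one case and a control weight of one, which balances all the matching factors, including practice and index date. It also avoids the extra parameters where events are few; Section 9 says: "We expect low number of occurrences for the outcomes of referrals for adjustment disorder and parasuicide/suicide".
- **After exclusions.** Apply the same rules after the Section 8.3 exclusions and in the Section 8.4 repeat.
- **Reporting.** Tabulate controls per case by ethnicity and IMD quintile, so that readers can see whether the problem arose.

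The cost is SAP wording and a few lines of R. The downsides are up to about 9 more parameters, slightly wider intervals, and the loss of incomplete sets where weighting is used.

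Separate minor point: for primary care encounters, specify robust or quasi-Poisson standard errors or a negative binomial model. The only remedy that Section 8.1 names, transformation, does not correct overdispersion.
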